8.1.3 Secondary Modified Analysis Datasets

(Secondary Modified Intent-to-Treat Samples, SmITTs)

The SmITTs datasets will be used in the secondary and additional analyses. Participants enrolled in the study who had baseline data and the endpoint data in question will be included. No imputation will be done for missing endpoints unless there is evidence that the endpoint is *missing for cause*. The reason that there are more than one SmITT data set is that the data set is dependent upon the endpoint in question; only those subjects with baseline and endpoint data *for that endpoint* will be included in the analysis.

8.1.4 Per Protocol Dataset

(Per-Protocol Sample, PP)

This will be a subset of the PmITT analysis dataset comprising participants without deviations from the protocol that affect the scientific soundness of the primary safety and effectiveness objectives (i.e., the ability to estimate the effectiveness of Renuvion in reducing submental laxity or to estimate its safety). Participants with protocol deviations that affect this ability will be identified at the data review meeting that takes place before database lock. The effectiveness and safety analysis will also be performed in this Per-Protocol population if the effectiveness and/or safety primary hypotheses are not passed.

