6.4.2. Follow-up Visits & Subject Contact outside of Follow-up Visits

Subjects will be asked to return to the study site at the following times post-procedure:

- 1 (+2) day
- 7 (± 1) days
- 14 (± 3) days
- 30 (± 7) days
- 90 (± 10) days
- 180 (± 15) days

Post-procedure assessments and 2D/3D photographic imaging will be performed during the follow-up visits. The same standardized photography views will be used throughout the study as documented in the image capture document developed for the study. **Table 1** illustrates study procedures that will occur at each visit.

Due to the challenges of COVID-19, if a subject is unable to return to the office for an in-person visit, follow-up visits will be conducted virtually. If a visit is completed virtually, missing assessments such as photographs will be documented as a protocol deviation specifically noting COVID-19. Outside of photographs, study investigators and study staff will ensure all other assessments related to each follow-up visit are completed virtually if the visit is done virtually. For virtual visits, the investigator and/or study staff completing the visit and assessments will be identified on the case report form; as well, the manner in which the visit was completed will also be marked on the Case Report Form (i.e. video call, phone call, etc.). Virtual visits should be done via video call if possible, to ensure subject identity. If a telephone call must be done, the investigator and/or study staff must positively identify the subject prior to conducting the virtual visit by requesting the subject to state their address and date of birth. Subjects will be strongly encouraged to come in (albeit safely) for their D180 visit; this visit is vitally important as this is the primary endpoint and photographic images are needed for many of the assessments. Only investigators and study staff who have been trained and delegated to conduct virtual visits as indicated on the delegation log may conduct virtual study visits.

Subjects may be seen for an unscheduled appointment at any time at investigator's discretion. Study staff will contact (phone, text, email, video call at subject's preference) all subjects with ongoing Adverse Events at the following time points, as applicable:

- 21 (± 5) days
- 45 (± 5) days
- 60 (± 5) days
- 75 (± 5) days
- 105 (± 5) days
- 120 (± 5) days
- 135 (± 5) days
- 150 (± 5) days
- 165 (± 5) days

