8 ANALYSIS POPULATIONS AND HANDLING MISSING DATA

8.1 Analysis Sets and Handling of Missing Data

8.1.1 Full Analysis Dataset

(Intent-to-Treat Sample, ITT)

The ITT sample will be used in the primary safety analysis. This is defined as the subjects who enrolled in the trial and on whom the procedure was initiated at least to the point where energy from Renuvion entered the subject’s skin.

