8.1.2 Primary Modified Analysis Dataset

(Primary Modified Intent-to-Treat Sample, PmITT)

The PmITT sample will be used in the primary effectiveness analysis. Participants enrolled in the study who had baseline photographs taken, completed the study procedure, and have at least one post-treatment photograph at or between 90 and 180 days will be included in the ITT sample.

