8.1.5 Imputation of Missing Values

Those with missing post-treatment photographs at the 180-day visit will have their last post-treatment photograph (such as the 90-day follow-up image) carried forward for use in the IPR assessment for the primary effectiveness endpoint. Since generally the appearance of lax tissue in the neck and submental regions will continue to improve for up to 180 days post-procedure, post-treatment photographs taken at a time point earlier than the 180-day visit will not show more improvement than the missing 180-day photographs. Therefore, the last-value-carried-forward (LVCF) imputation is conservative.

For those subjects with missing primary endpoint data at the 180-day visit and no follow-up images available to carry-forward, the primary effectiveness objective will have the missing data multiply imputed using the patient's baseline characteristics and follow-up evaluations before and after the missing data.

The primary effectiveness hypothesis test will use this data set with a combination of LVCF and multiply imputed values carried out on the PmITT analysis set.

Those with missing endpoint data at the 7-day FUV for the primary safety objective will have the missing data multiply imputed using the patient's baseline characteristics and follow-up evaluations before and after the missing data. The primary safety hypothesis test will use this data set carried out on the ITT analysis set.

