9.3 Statistical Analysis of Primary Safety Endpoint

NRS Pain through the 7-day Follow-up Visit

The 11-point NRS is used to measure facial, submental, and neck pain prior to procedure, within 60 minutes of treatment and at all follow-up visits. Note that the pain scale is 11 points: 0 through 10. The 0 value represents no pain. Levels 1 through 5 represent mild pain and levels 6 and 7 represent moderate pain. Patients who experience pain no higher than 7 through the 7-day visit post-procedure will be classified as “acceptable pain” patients.

For the primary safety endpoint, the proportion of patients with acceptable pain (P) will be tested against the PG. If the lower bound of the two-sided 95% confidence interval of the proportion of subject achieving treatment successes is greater than the Performance Goal, the primary safety endpoint would be met. The statistical test will be a one-sided Fisher’s Exact Test at $\alpha = 0.05$. For the primary safety endpoint to be met, H_0 must be rejected.

$$H_0: P \leq 55\% \quad \text{vs.} \quad H_a: P > 55\%$$

Standard descriptive statistics will also be reported; see **Section 9.1** for a list of descriptive statistics.

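### The supportive per-protocol safety analysis excludes subjects with complete pain scores through day 7 if they have no day 90 to 180 photograph

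*SAP*

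**What the plan says.** - **Per-protocol set (SAP 8.1.4).** There is one set for both primary objectives: "This will be a subset of the PmITT analysis dataset comprising participants without deviations from the protocol". Its use is conditional: "The effectiveness and safety analysis will also be performed in this Per-Protocol population if the effectiveness and/or safety primary hypotheses are not passed".
- **PmITT (SAP 8.1.2).** Members must have baseline photographs, have completed the procedure and "have at least one post-treatment photograph at or between 90 and 180 days". The sentence ends by naming the ITT sample, where PmITT is evidently meant.
- **Primary safety population (SAP 8.1.1).** "The ITT sample will be used in the primary safety analysis". ITT needs enrolment and delivery of device energy to the subject. It has no photograph condition. SAP 8.1.5 confirms this: "The primary safety hypothesis test will use this data set carried out on the ITT analysis set".
- **Safety endpoint (SAP 9.3).** "Patients who experience pain no higher than 7 through the 7-day visit post-procedure will be classified as" having acceptable pain. The endpoint rests on pain scores alone and is settled at the 7-day visit.
- **Virtual visits (Protocol 6.4.2, follow-up visits).** When a visit is held virtually, photographs are missed but the rest goes ahead: "Outside of photographs, study investigators and study staff will ensure all other assessments related to each follow-up visit are completed virtually".

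**The concern.** The photograph condition suits effectiveness, which is judged from images. Applied to pain, it makes membership of the safety analysis depend on something that happens at least 80 days after the outcome is known. A subject who leaves between day 7 and day 90, or whose day-90 and day-180 visits are both virtual, can have a full pain record and no relevant deviation and still be excluded.

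Elsewhere the SAP avoids this. ITT carries no photograph condition, and the sets for secondary and additional analyses (SAP 8.1.3) ask only for baseline data and data on the endpoint concerned. Only the per-protocol definition applies an imaging condition to a pain endpoint.

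What is at stake is how a supportive result is read. One trigger for the analysis is a failed ITT safety test, which is when a more favourable per-protocol figure would be most likely to be cited. If the excluded subjects differ in pain from those retained, that figure is distorted.

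**Working it through.** **1. Who is excluded.** Take a subject who received the full procedure, has all pain scores through day 7, and has no photograph from day 90 to day 180.

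| Set | Condition that decides | Included? |
|---|---|---|
| ITT (SAP 8.1.1) | energy delivered | yes |
| PmITT (SAP 8.1.2) | day 90 to 180 photograph | no |
| Per-protocol (SAP 8.1.4) | must be in PmITT | no |

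The exclusion follows from the definitions and needs no arithmetic.

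**2. The plan's own figure.** Inputs from SAP 7.1.1, applied to safety by SAP 7.1.2: performance goal 0.55, assumed true proportion 0.75, one-sided alpha 0.025, N=60, reject at 41 or more successes. With X binomial:

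- Size: P(X ≥ 41 | 60, 0.55) = 0.0246.
- Power: P(X ≥ 41 | 60, 0.75) = 0.9075, which matches the stated 0.90752.

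**3. Cut-offs if k subjects lack the photograph.** The documents do not give k, so it is an assumption. The planned allowance is 65 − 60 = 5. The cut-off is the smallest r with P(X ≥ r | 65 − k, 0.55) ≤ 0.025.

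| k | N | Cut-off | Power at 0.75 |
|---|---|---|---|
| 0 | 65 | 45 | 0.887 |
| 2 | 63 | 43 | 0.914 |
| 5 | 60 | 41 | 0.908 |
| 10 | 55 | 38 | 0.877 |

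Power stays between 0.877 and 0.914 at these values, so the issue is not precision. It is which subjects are counted.

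**4. Effect on a near-threshold result.** p = P(X ≥ x | N, 0.55). Complete pain data are assumed, and exclusions for other deviations are ignored.

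| Subjects lost (assumed) | All 65 treated | Per-protocol | At one-sided 0.025 |
|---|---|---|---|
| 5, all severe pain | 42/65, p=0.075 | 42/60, p=0.013 | not passed, then passed |
| 1, severe pain | 44/65, p=0.0255 | 44/64, p=0.017 | not passed, then passed |
| 5, all acceptable pain | 45/65, p=0.014 | 40/60, p=0.045 | passed, then not passed |

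In the third row ITT safety passes, so the per-protocol run would take place only if the effectiveness hypothesis was not passed.

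**5. Dependence on alpha.** SAP 9.3 states one-sided alpha 0.05 beside a two-sided 95% confidence interval rule, which corresponds to 0.025. At 0.05 the first row still changes from not passed to passed. The second does not change, because 44/65 already passes. The third does not change, because 40/60 also passes.

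**6. How extreme the illustrations are.** If photograph loss is unrelated to pain, the chance that all five lost subjects come from one group is:

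- Severe pain, 65 − 42 = 23 of 65: C(23,5)/C(65,5) = 33,649/8,259,888 = 0.4%.
- Acceptable pain, 45 of 65: C(45,5)/C(65,5) = 1,221,759/8,259,888 = 14.8%.

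**The case against.** The strongest reply is that little depends on this analysis. The primary safety test is on ITT, and SAP 9.3 requires the null hypothesis to be rejected for the endpoint to be met. The per-protocol run is conditional, and SAP 8.1.4 presents it as an addition. SAP 8.1.8 also requires the reasons for exclusion from the mITT and per-protocol samples to be examined and reported. All of this stands. A reader might infer that these subjects are removed from the safety evaluation, or that a per-protocol pass could rescue a failed ITT test. The documents support neither reading.

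A reader might also infer that the rule favours the device because subjects in severe pain drop out. No document links early pain to later loss. Protocol 7.5 makes moderate and severe pain adverse events, and Protocol 8.1 adds staff contacts at days 21, 45, 60 and 75 while an event is ongoing, which could improve retention. Photographs missed through virtual visits have no evident tie to pain. The direction is therefore unknown.

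PmITT also requires a completed procedure. That is an ordinary per-protocol condition, because it concerns the treatment received, and it is no part of this point.

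Finally, SAP 8.1.5 plans multiple imputation on PmITT for subjects with no image to carry forward, whom SAP 8.1.2 appears to exclude. If SAP 8.1.5 governs, PmITT is wider and fewer subjects are affected. This limits the size of the problem but leaves membership of the per-protocol set unclear.

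What remains is that, on the wording of SAP 8.1.2 and 8.1.4, an imaging condition decides who counts in a pain analysis.

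**Conclusion.** The point holds for the supportive per-protocol safety analysis only. Read as written, SAP 8.1.2 and 8.1.4 exclude subjects with complete pain data through day 7 for a later reason unrelated to pain. The primary ITT safety conclusion does not change.

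The size cannot be fixed from the documents, because neither the number of subjects without a photograph nor their pain is known. With the planned allowance of five losses, a result near the cut-off can move in either direction at one-sided 0.025. Those examples assume that all five lost subjects are in the same pain group, which is unlikely for the severe-pain case if loss is unrelated to pain. They also use the one-sample exact binomial test of SAP 7.1.1, and the 0.05 level in SAP 9.3 would alter some near-threshold cases.

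This is a modest defect in a secondary analysis. It is worth correcting before database lock because the correction is simple and removes a selection that would be hard to defend afterwards.

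**What to change.** Amend SAP 8.1.4 to define two sets:

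- **Effectiveness per-protocol:** a subset of PmITT, as now.
- **Safety per-protocol:** a subset of ITT with no photograph condition, excluding only subjects with deviations that affect delivery of the study procedure or pain assessment through day 7.

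Add that per-protocol results are supportive and do not replace the ITT conclusion. In the same edit, correct the set name at the end of SAP 8.1.2 and reconcile SAP 8.1.2 with SAP 8.1.5 on whether subjects with no usable follow-up image belong to PmITT.

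The cost is a few sentences in the SAP. It needs no new data, visits or subjects.

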8.1.5 Imputation of Missing Values

Those with missing post-treatment photographs at the 180-day visit will have their last post-treatment photograph (such as the 90-day follow-up image) carried forward for use in the IPR assessment for the primary effectiveness endpoint. Since generally the appearance of lax tissue in the neck and submental regions will continue to improve for up to 180 days post-procedure, post-treatment photographs taken at a time point earlier than the 180-day visit will not show more improvement than the missing 180-day photographs. Therefore, the last-value-carried-forward (LVCF) imputation is conservative.

For those subjects with missing primary endpoint data at the 180-day visit and no follow-up images available to carry-forward, the primary effectiveness objective will have the missing data multiply imputed using the patient's baseline characteristics and follow-up evaluations before and after the missing data.

The primary effectiveness hypothesis test will use this data set with a combination of LVCF and multiply imputed values carried out on the PmITT analysis set.

Those with missing endpoint data at the 7-day FUV for the primary safety objective will have the missing data multiply imputed using the patient's baseline characteristics and follow-up evaluations before and after the missing data. The primary safety hypothesis test will use this data set carried out on the ITT analysis set.

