7.4 Subject Diary

Study subjects will be asked to complete a daily diary (see **Appendix B**) starting from the procedure date (after study procedure, at home) until the 14-day follow-up visit to complete daily 11-point NRS pain assessments and document any complications they have experienced.

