APPENDIX B: SAMPLE STUDY SUBJECT DAILY DIARY*To be completed by study staff:*

Site ID #	Subject ID	Subject Initials	Procedure Date		
					
			First/Middle/Last	Day	Month
					Year

Instructions to subjects:

Please use this form to record any complications after your study procedure. Be sure to complete an entry every day until your 14-day follow-up visit. Please bring this form to your 14-day follow-up visit.

Day X	Date:										
Please rate the average pain you are experiencing in the treatment area on a scale of 0-10, with 0 being 'Best/No Pain' and 10 being the 'Worst Possible Pain'. Please check one box.											
	0	1	2	3	4	5	6	7	8	9	10
Pain											
Please check all boxes that apply to record any expected treatment effects that you are experiencing.											
Expected Treatment Effect	Are you experiencing this event?					Is this causing an impact to your daily activities such as work, sleep, driving, appetite, etc.?					
Swelling		YES		NO			YES		NO		
Redness of the skin		YES		NO			YES		NO		
Bruising		YES		NO			YES		NO		
Touch sensitivity, numbness/tingling, itching		YES		NO			YES		NO		
Firm areas under the skin		YES		NO			YES		NO		
Crackling sound or popping feeling under the skin		YES		NO			YES		NO		
Are there any other complications you are experiencing?	 YES*  NO *If "YES", please call your study doctor to discuss.										
Are you wearing your compression garment 22 hours/day for Days 0 – 3 and at night for Days 4-21 as directed by the Post-Procedure Care Instructions?							 YES  NO				

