5 EVALUATION TOOLS

The following evaluation tools will be used in this study:

- 2-Dimensional and 3-Dimensional Photography
- Independent Photographic Assessments
- Quantitative Assessment of Lift
- Quantitative Assessment of Volume
- Modified Global Aesthetic Improvement Scale (GAIS)
- Subject Satisfaction Survey
- Numeric Rating Scale (NRS) for pain
- Subject Diary
- Adverse Event Reporting
- TEN Testing of Sensory Nerves
- Examination of Facial Motor Nerves
- Burn Depth Assessment (Burn Adverse Events Only)

More information about the evaluation tools, including how to administer them, is included in the study protocol. The schedule on which they are administered is provided in **Table 1**.

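### A missing 7-day pain score goes straight to multiple imputation, although the daily diary asks the same 0-10 question on day 7; the recorded answer should be used first.

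*SAP*

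**What the plan says.** **Missing data rule.** SAP 8.1.5 states: "Those with missing endpoint data at the 7-day FUV for the primary safety objective will have the missing data multiply imputed". The model is to be built "using the patient's baseline characteristics and follow-up evaluations before and after the missing data. The primary safety hypothesis test will use this data set". The diary is not mentioned there, nor in the tipping-point sections (SAP 8.1.6 and 8.1.7).

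**Endpoint.** SAP 9.3 sets the criterion as follows: "Patients who experience pain no higher than 7 through the 7-day visit post-procedure will be classified as" acceptable pain. Protocol 4.3.2 ties it to three occasions: immediately after the procedure, the 1-day visit and the 7-day visit.

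**Diary.** Protocol 7.4 asks subjects to keep a diary from the procedure date "until the 14-day follow-up visit to complete daily 11-point NRS pain assessments". The form in Protocol Appendix B instructs: "Be sure to complete an entry every day until your 14-day follow-up visit". Its pain item begins "Please rate the average pain you are experiencing in the treatment area on a scale of 0-10", and the direction for the visit scale in Protocol 7.5 has the same wording and the same end-point labels. The diary reaches the site at day 14: "Please bring this form to your 14-day follow-up visit".

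**Role of the diary in the SAP.** SAP section 5 lists it among the evaluation tools. No SAP section then gives it a part in the endpoint, the imputation or the sensitivity analysis.

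**The concern.** Multiple imputation is meant for values that nobody knows. A subject who misses the 7-day assessment but hands in a complete diary a week later has answered the endpoint question, on the endpoint scale, for that day. Under SAP 8.1.5 that answer is not the value analysed. Even if diary scores entered the model as predictors, the analysed value would still be a draw around them, so a subject who wrote 9 on day 7 could be counted as acceptable in some imputations, and one who wrote 1 as severe.

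The same section treats effectiveness differently. A missing 180-day photograph is first replaced by an actual earlier photograph, and imputation is kept for subjects who have none. Safety has no such observed-data step, although its substitute would be closer in time: the same day or within one day, against a photograph that may be some 90 days older.

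At stake are the classification of a few subjects on a primary endpoint, and a larger share of imputed values for the tipping-point analysis to carry than the data require.

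**Working it through.** **1. Is a usable observation available?**

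| Item | Visit score | Diary |
|---|---|---|
| Source | Protocol 7.5 | Protocol 7.4, Appendix B |
| Question | Average pain in the treatment area, 0-10 | Same wording |
| Timing | Day 7, window 6-8 | Daily, day 0 to the 14-day visit |
| Role in the SAP | Primary safety endpoint | Listed as a tool, no analysis role |

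The diary covers day 7 and the whole 6-8 day window. It helps only a subject who (a) has no 7-day visit score, (b) made an entry on days 6-8, (c) returned the diary, and (d) has no earlier endpoint score above 7, since such a subject has already failed.

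**2. The plan's own figure.** SAP 7.1.1, applied to safety by 7.1.2, gives N = 60, rejection at 41 or more successes, goal 55%, assumed rate 75%, one-sided alpha 0.025 and power 0.90752. With X binomial:

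- P(X ≥ 41 | n = 60, p = 0.55) = 0.0246
- P(X ≥ 41 | n = 60, p = 0.75) = 0.9075

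The figure reproduces.

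**3. The boundary for the safety set.** The ITT set is every subject who received energy, so up to 65.

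- At one-sided 0.025: P(X ≥ 44 | 65, 0.55) = 0.0255 is too large and P(X ≥ 45 | 65, 0.55) = 0.0136, so 45/65 (69.2%) is needed. Power at 75% is 0.887.
- At one-sided 0.05: P(X ≥ 43 | 65, 0.55) = 0.0450, so 43/65 (66.2%) is needed. Power at 75% is 0.960.

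SAP 9.3 states alpha 0.05 for safety and also requires the lower limit of a two-sided 95% interval to exceed the goal, which corresponds to 0.025. Both boundaries are therefore carried here.

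**4. Weight of one subject.** 1/65 = 1.5 percentage points. Such a subject decides the test only if the other 64 fall exactly one short of the boundary:

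- boundary 45: P(X = 44 | 64, 0.75) = 0.057
- boundary 43: P(X = 42 | 64, 0.75) = 0.026

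Even then the result changes only if the imputation disagrees with the diary.

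**5. Bounds for m missing scores.** The documents do not give m, so 1 to 5 is an assumption (1/65 = 1.5 to 5/65 = 7.7 points). With boundary 45 and a 75% rate in the remaining subjects, the lower bound sets all m to failure, P(X ≥ 45 | 65 − m), and the upper sets all m to success, P(X ≥ 45 − m | 65 − m):

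| m | All failures | All successes |
|---|---|---|
| 1 | 0.844 | 0.901 |
| 2 | 0.791 | 0.914 |
| 3 | 0.726 | 0.926 |
| 5 | 0.569 | 0.946 |

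These are extremes, not the expected effect of multiple imputation. The value m = 5 uses up the entire 65 − 60 allowance for losses, which is meant to cover 180 days, so it is a high figure for day 7.

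**The case against.** **Missing scores should be rare.** Protocol 6.4 moves a visit to video or telephone when the subject cannot attend, and requires everything except photographs to be completed. Subjects lost before day 14 do not return a diary at that visit, so it may not help for them. This stands, and it keeps the effect small.

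**The imputation model is not blind.** It uses evaluations before and after the gap, which include the 1-day and 14-day visit scores and could be read to include neighbouring diary days. This also stands. A reader might infer that a subject with a severe diary score would be drawn as acceptable in about three of four imputations, from the 75% design rate. The documents do not support that: it ignores those predictors, and 75% is the assumed rate for the whole-week criterion, not for a single day-7 score. Nor do they support an inference that the diary could replace most of the imputed values, since no completion or return rate is given.

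**The tipping-point analysis already guards the result.** In part. It turns imputed values into failures one at a time, so it bounds the error that favours the device, but it runs only after a rejection. It does nothing for a subject wrongly drawn as severe, and it can set to failure a subject whose diary shows 1.

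**A home score is not a visit score.** If the endpoint is strictly the score at the visits named in Protocol 4.3.2, declining to substitute is a defensible choice. But a draw from a model is not a visit score either, and the SAP gives no sign that the choice was considered.

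**Conclusion.** The point holds for a narrow group: subjects with no 7-day visit score, a diary entry in the 6-8 day window, a returned diary and no earlier failure. For them the SAP puts imputation draws where an observed answer to the same question exists.

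The size is 1.5 percentage points per subject, and it matters only near 45/65, or 43/65 if alpha 0.05 governs. At the design rate one such subject could be decisive in at most about 6% of trials at the first boundary and 3% at the second. No sample size, alpha or planned power figure changes. A reader might infer that the primary safety conclusion is unsound; the documents do not support that. The change is still worth making before the data are seen, because choosing between diary and imputation afterwards would be a data-driven decision on a primary endpoint.

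**What to change.** In SAP 8.1.5, before the sentence on imputing the 7-day safety data, insert:

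> *If the 7-day visit NRS score is missing, the day-7 diary NRS entry is used; if that is absent, the single diary entry closest to day 7 within days 6-8 is used (the later day if tied). Multiple imputation and the tipping-point analysis apply only to subjects with neither a visit score nor a diary entry in that window.*

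A single entry is named on purpose. Attending subjects contribute one score at this visit, so taking the highest of up to three diary entries would hold the substituted subjects to a stricter standard.

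The cost is this addition and use of diary scores that the study already collects. The small drawback is that the substituted score is recorded at home and depends on the diary being completed and returned.
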